# **3. OBJECTIVES AND OUTCOME MEASURES**

### 3.1 Primary Objective

To establish the efficacy of a strategy of early aneurysm treatment (within 72h of ictus) in a population of World Federation of Neurosurgical Societies grade 4-5 (high grade) aneurysmal subarachnoid haemorrhage (aSAH) patients in comparison with the conventional strategy of treatment of aneurysm after neurological improvement (to WFNS grade 1-3).

### 3.2 MRI sub-study Objective (in 100 participants)

To explore whether brain Magnetic Resonance Imaging (MRI) markers in patients with high [4-5] grade aSAH are related to outcome, and whether they might be used to identify patients who would benefit from each treatment strategy – i.e. to stratify the management of grade 4-5 aSAH patients.

### **3.3 Primary Endpoint/Outcome**

Primary outcome is functional outcome at 12 months determined by ordinal analysis of modified Rankin score (mRS). Ordinal analysis results in substantially greater statistical power to detect a treatment effect. mRS is a widely-used outcome measure in stroke (including aSAH) and is based on the ability to carry out usual day to day activities. Score ranges from 0 (no symptoms or disability) to 6 (death).

[figure not shown]
### 3.4 Secondary Endpoints/Outcomes

[figure not shown]
- Dichotomised mRS: 0-3 vs 4-6; 0-2 vs 3-6
- Mortality rate (30 days and 12 months; survival analysis will be undertaken)
- Re-bleeding rate from randomisation
- Treatment related complication rate and SAE report rates reported as per standard CTU procedures. All SAEs, and their relatedness to treatment, will be added to the CRF and followed until resolution.
- Time in hospital to discharge and length of ITU and HDU stay
- mRS at discharge
- Functional outcome at six months determined by ordinal analysis of modified Rankin score (mRS)

[figure not shown]
### 3.5 MRI sub-study Outcomes

- Lesion load on DWI
- Fractional anisotropy values on DTI
- Brain perfusion and CSF parameters
- Endothelial permeability
- Blood-brain barrier integrity on MRI

# 4. TRIAL DESIGN

# **5. STUDY SETTING**

This is a study of patients admitted with WFNS grades 4 and 5 aneurysmal SAH. As these patients usually have depressed GCS they frequently require airway protection and ventilation. Therefore all patients considered for recruitment in this study are likely to be admitted to an intensive therapy unit or neuro high dependency unit (ITU/HDU). In neurosciences centres these patients are likely to be in neuro ITU rather than general ITU, for management by a specialist neuro critical care team. Patients who are randomised to the early treatment arm are likely to remain in ITU/HDU prior to aneurysm treatment. Some patients who are randomised to the treatment after neurological recovery arm may be discharged from ITU/HDU prior to aneurysm treatment. However, as a large number of patients with high-grade SAH have multi-system disorders such as cardio-respiratory insufficiency, it is expected that a substantial proportion of patients randomised to the treatment after recovery arm will remain in ITU/HDU for a substantial proportion of their hospital stay, prior to aneurysm treatment.

# **6. ELIGIBILITY CRITERIA**

### 6.1 Inclusion Criteria

- Aged 18-80 years
- WFNS grade 4 or 5 aSAH (grade for trial eligibility purposes is the WFNS grade recorded at first medical assessment following: hospital attendance AND confirmation of the diagnosis of SAH – by CT (or MRI) and/or lumbar puncture)
- Assent obtained from next of kin, professional consultee or welfare attorney/nearest relative

BEFORE INCLUDING A PARTICIPANT IN THE TRIAL, IT MUST ALSO BE CONFIRMED THAT IT WILL BE POSSIBLE TO TREAT THE PARTICIPANT WITHIN 72 HOURS OF ICTUS, SHOULD THEY BE RANDOMISED TO THE EARLY TREATMENT ARM.

### 6.2 Exclusion Criteria

- Age < 18 or > 80 years
- WFNS grade 1-3, or uncertain WFNS grade (where patient recovers quickly and proves not to be of true high grade)
  - Patients of uncertain grade on transfer to a neuroscience unit where a formal sedation hold is undertaken at the neurosciences centre and the patient is established to be truly grade 4 or 5 will be eligible for trial
  - This will also apply to patients of uncertain grade undergoing sedation hold after insertion of external ventricular drain (EVD) or other early intervention for hydrocephalus
- Signs of coning or brain death not promptly reversed by anti-cerebral oedema treatment
- Pure intraventricular haemorrhage (no SAH)
- Large intracerebral haematoma which requires immediate clot evacuation
- Significant aneurysmal SAH-related haemodynamic instability
- Lack of clinical equipoise
- Lack of assent/consent
- Pregnancy
- Pre SAH modified Rankin score >2
- Pre-existing severe co-morbidity such that clinical follow up at 12 months is judged unlikely
- Non-saccular, Mycotic, giant or other atypical aneurysm

For MRI sub study only

• Known absolute contra indication to MRI

# **7. TRIAL PROCEDURES**

### 7.1 Recruitment

Once a high grade SAH patient is admitted to neuroITU/HDU (or equivalent) in a trial centre, the patient will be stabilised from neurological and cardio-respiratory points of view as per local protocol. If the patient was initially admitted to a different hospital, confirmation of the WFNS grade prior to intubation/ventilation will be sought from the referral letter or by directly contacting the referring team. If the WFNS grade before the patient was intubated/ ventilated could not be established, the patient will be considered to be of uncertain grade (WFNS U) and will be ineligible for the study unless subsequent formal sedation hold and re-assessment confirms high grade. However, there will be no requirement in the trial centre to confirm the patient's WFNS grade by reversing sedation in ITU. Once aneurysmal SAH is confirmed and the patient is stable, the admitting neurosurgical/anaesthetic team will assess the patient with regard to eligibility for the trial.

### 7.2 Consent

An appropriate clinician (ITU consultant/registrar, neurosurgical consultant/registrar or interventional neuroradiology consultant/registrar) with documented responsibility on the delegation log, will discuss the trial and provide written Participant Information Sheet). The PI is responsible for ensuring that informed assent for study participation is given by each patient's NOK or relative, or by a nominated consultee, for patients fulfilling TOPSAT 2 eligibility criteria. A delegated individual will then return after an appropriate interval (maximum four hours) to allow adequate time for reflection, and obtain assent for the trial from the appropriate consultee.

The consent process for England/Wales/Northern Ireland and Scotland are detailed below.

#### England, Wales and Northern Ireland

The incapacitating nature of the condition precludes obtaining prospective informed consent from all, or nearly all, participants. Wherever possible we will aim to establish the views of the patient with regard to involvement in research from a Personal Consultee (England/Wales) or Next of Kin (Northern Ireland). However, given the time pressures of the study, this process should not cause unnecessary delay. If no Personal Consultee/NOK can be identified, then the researcher must nominate a person who has no connection to the study, who is not listed on the delegation log, and who is willing to be consulted about the participation of the person who lacks capacity, to act as a Consultee, usually the ITU consultant. For patients in England and Wales, the nominated Professional/Personal Consultee will complete a Consultee Declaration Form, which will be countersigned by the PI or delegated personnel. For patients in Northern Ireland, a Close Relative/friend Assent Form will be completed and countersigned by the PI or delegated personnel.

The original signed Consent/Declaration/Assent Form and a copy of the Participant Information Sheet will be retained in the Investigator Site File (ISF), with copies provided to the Personal Consultee/NOK or Nominated Consultee and clinical notes. A copy will also be sent to the Newcastle Clinical Trials Unit for central monitoring purposes.

#### Scotland

Consent will be sought from a Relative/Welfare Attorney during a face-to-face meeting. In the event that a Relative/Welfare Attorney is unable to attend immediately, verbal consent will be obtained in a telephone conversion. This will be documented on a telephone consent form and countersigned by the PI or delegated personnel and witnessed by a second member of staff and should be recorded in the clinical notes. The Relative/Welfare Attorney will provide written consent at the next available opportunity.

If necessary, NHS translation services will be utilised to discuss the trial. Written informed consent should always be obtained prior to randomisation and prior to study specific procedures or investigations.

#### Non-UK sites

Comparable consent processes will take place in each of the following non-UK countries; any significant differences to this process will be discussed and noted at the SIV visits.

- Czech Republic
- Latvia
- Lithuania
- Estonia
- Poland
- Hungary
- Romania

The right to refuse to participate without giving reasons must be respected.

### 7.3 Regaining capacity

If a participant regains mental capacity they should be fully informed about the study and their consent sought to continue in it. If they do not wish to remain in the study they must be withdrawn. Any data collected so far will be retained and analysed unless they refuse consent, in which case these must be destroyed. This is in accordance with the Mental Capacity Act 2005 in England and Wales and The Adults with Incapacity (Scotland) Act 2000 in Scotland. In Northern Ireland this is currently governed by common law. This also applies if the consultee makes the decision to withdraw a participant from the study before they regain capacity.

A fully anonymised screening log will be completed at each site, recording the number of patients assessed, the number meeting inclusion criteria, WFNS grade, time from ictus to admission, the number excluded and reason(s). Screening logs will be sent to NCTU monthly.

A record will be kept of the actual intervention carried out and the time and date received, in both arms. Consent/assent will be sought from the participant/consultee to inform the patient's GP by letter about their participation in the trial as soon as practicable following the intervention.

### 7.4 Randomisation

Randomisation will be carried out by the research team at sites through the use of a web-based system accessed via the trial website (www.topsat2.co.uk), and hosted by the Health Services Research Unit, University of Aberdeen. This service is available 24/7. Further information is

available in the randomisation SOP. The randomisation will utilise a minimisation algorithm with 80% chance of being allocated to the minimisation group to reduce differences in two arms with respect to the following (with 20% following a totally random allocation):

- Grade 4 and 5 (so distributed equally in the two arms)
- Participant age at the time of randomisation (age bands 18-50, 51-65 and 66-80)
- Presence of clinically significant hydrocephalus requiring CSF drainage procedure (yes/no)
- UK/non-UK centre.

The randomisation service will automatically confirm randomisation details to the person carrying out the randomisation, and NCTU, by email.

If the patient is randomised to the early treatment arm, the result of randomisation will be communicated to the neurovascular team who will treat the aneurysm. They will decide on the most appropriate treatment strategy but, as per the RCT evidence base, if the aneurysm is technically amenable to coiling, coiling will be the initial therapeutic option. The usual institutional surgical consent form for the procedure will then be completed and the aneurysm must be treated within 24 hours of randomisation, and 72 hours of ictal bleed that led to hospital admission.

If the patient is randomised to the treatment after neurological improvement arm, the result will be communicated to the ITU and neurovascular team who will carry on managing the patient as per established protocol. Once the patient's neurological status improves to WFNS grade 3 or better (or GCS 13-15 or equivalent if WFNS is not assessed), the aneurysm will be treated expeditiously (by coiling, if technically amenable to coiling). According to the natural history of the disease, this improvement may take several weeks and in some may never happen. On the contrary, in some cases this may happen soon after randomisation if the patient's improvement is rapid. There will be no specific time-delay criterion for aneurysm treatment in this arm. However, it is anticipated that aneurysm treatment beyond one month post-randomisation would be exceptional; both due to the lower risk of re-bleeding after that time and the very guarded prognosis if a patient has not recovered sufficiently neurologically for treatment within one month.

A record will be kept of the actual treatment received and the date on which received, in both arms. With the patients' consent their GPs will be informed by letter about their participation in the trial.

### 7.5 Blinding

Treatment allocation in TOPSAT 2 is not blinded. However follow-up for functional recovery at six and 12 months by postal questionnaire will be blinded to the participant's treatment allocation. The Trial Secretary responsible for entering questionnaire data will therefore be blinded to allocation. This follows the successful ISAT and STICH trials methodology.

Individuals carrying out assessments of MRI scans for those participants in the MRI sub-study will be blinded to treatment allocation.

### 7.6 Baseline Assessments and Data

Baseline data will include collection of the following information:

- WFNS grade
- Demographic data, including age and co-morbidities
- Hydrocephalus requiring drainage
- Estimated modified Rankin Scale prior to ictus
- Date and time of ictal bleed leading to admission/diagnosis
- Admission data, including GCS prior to intubation/ventilation, Fisher grade and hydrocephalus on admission CT

### 7.7 Trial Assessments

Assessments to be conducted on day of aneurysm procedure

- Details of procedure carried out, date and time
- Adverse events
- Details of any additional procedures carried out
- WFNS grade

#### Day 30

• Mortality data to be collected, to include date and cause of death

#### Six and 12 months

- Modified Rankin scale questionnaire
- EQ5-D
- Mortality data (at 12 months)

7.7.1	Schedule of Events

Time	Screening	Consent and Randomisation	MRI (in MRI substudy centres only)	Treatment within 24hrs of randomisation OR after neurological recovery (depending on treatment allocation)	Discharge (or day 30 if still in- patient)	6 months	12 months
			After consent, before treatment for aneurysm and within 72 hours of ictus			+6 months following ictus (+/- 2 weeks)	+12 months following ictus (+/- 2 weeks)
Study discussed/ PIS given	х						
Assent		х					
Randomisation		х					
MRI scan (in MRI sub-study centres only)			Х			Xa	
Aneurysm treatment				x			
mRS/EQ5-D (at 6 and 12 months; by post or online as per participant preference)					X (by Research Nurse)	X (Postal)	X (Postal)
Adverse events				x	Х	х	х

a) Routine MRI scan performed at 5-6 months post-surgery as per routine clinical practice

## 7.8 Withdrawal Criteria

Participants have the right to withdraw from the trial at any time without having to give a reason. Site staff should try to ascertain the reason for withdrawal and document this in the Case Report Form and participant's medical notes.

An Investigator may discontinue a participant from the trial at any time if he/she considers it necessary for any reason including:

- Participant withdrawal of consent
- Significant protocol deviation or non-compliance
- Investigator's discretion that it is in the best interest of the participant to withdraw
- Termination of the clinical trial by the sponsor

Where a participant withdraws from the trial whilst recruitment is active, an additional participant will be recruited.

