# **10. STATISTICAL CONSIDERATIONS**

## **10.1** Analysis Population

The aim is to collect outcome on all patients randomised to the study who do not withdraw consent.

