#### Statistical Analysis

The Statistical Analysis Plan will be published prior to the completion of recruitment and data analysis. All randomised patients will remain in the trial whether they receive the allocated treatment or not, and will be accounted for in the final analysis. The trial is powered to account for a certain level of cross-over and drop-out from follow-up, based on ISAT/HELPS trials experience, predominantly in UK aSAH subjects. It is anticipated that there will be very few crossovers from early treatment allocation but there may be some from "treatment on neurological recovery" to "early treatment" arm – we have estimated 2% based on the TOPSAT pilot and other UK led trials involving coiling. Loss to primary outcome follow-up in ISAT at one year was 1%. In the HELPS trial for UK SAH subjects it was <2% at 18 months. We anticipate a similar or lower level of loss in TOPSAT2, particularly as the principal outcome at grades 4 and 5 will be mortality. Fairly complete death ascertainment from combined primary and secondary care electronic records is anticipated, but letter/telephone contact with a GP followed by death certification will be pursued, should any uncertain cases be identified.

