It is inevitable that a significant number of the subjects recruited into TOPSAT 2 will die before hospital discharge, and many survivors will make only a limited recovery. Information sheets for appropriate consultees and discussions with them will make the prognosis of grade 4-5 aSAH clear. It will be made clear verbally and in the PIS that participants have the right to withdraw from the study at any time for any reason, and without giving a reason. It is understood by all concerned that an excessive rate of withdrawals can render the study uninterpretable; therefore, unnecessary withdrawal of patients should be avoided. Should a patient decide to withdraw from the study, all efforts will be made to report the reason for withdrawal as thoroughly as possible. Consent will be sought to retain data collected up to the point of withdrawal. Patients who withdraw and want all data deleted can be replaced if recruitment remains ongoing.

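### Section 7.8 lets an unblinded investigator discontinue participants from the trial for protocol deviation and replaces withdrawals, contradicting 10.1 and 10.3 on retention and 10.2.1 and 13.1 on replacement

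*Protocol*

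**What the plan says.** **Who may leave the trial.** Protocol 7.8 reads: "An Investigator may discontinue a participant from the trial at any time if he/she considers it necessary for any reason including". The listed reasons include "Significant protocol deviation or non-compliance" and the investigator's view of the participant's best interest. The section speaks of leaving the trial. It does not separate leaving the allocated strategy from leaving follow-up. Under 7.5, "Treatment allocation in TOPSAT 2 is not blinded"; only the postal follow-up is blinded.

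**Who is to be followed and analysed.** Section 10.1: "The aim is to collect outcome on all patients randomised to the study who do not withdraw consent". The Statistical Analysis paragraph at the end of 10.3: "All randomised patients will remain in the trial whether they receive the allocated treatment or not, and will be accounted for in the final analysis". Section 10.2.1 calls the analysis modified intention-to-treat, drops patients lost to follow-up from the primary analysis (with a sensitivity analysis for missing data), uses data up to withdrawal unless refused, and adds a per-protocol analysis.

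**Who is replaced.** Section 7.8: "Where a participant withdraws from the trial whilst recruitment is active, an additional participant will be recruited". Section 13.1: "Patients who withdraw and want all data deleted can be replaced if recruitment remains ongoing". Section 10.2.1 likewise ties replacement to refusal of data use.

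**The concern.** In a trial of two timing strategies, treatment outside the allocated strategy is the most obvious protocol deviation. Section 7.8 makes a significant deviation a ground for discontinuation from the trial; 10.3 says such a patient stays. Site staff deciding whether to keep following a patient will turn to 7.8, not to the statistics section.

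What is at stake is the primary outcome. A participant discontinued alive before 12 months and not followed has no 12-month mRS, and 10.2.1 then takes that participant out of the primary analysis. The loss is unlikely to be random. The investigator knows the allocation. The early arm has fixed time limits, while treatment in the other arm depends on neurological improvement (7.4), so deviations arise from clinical course and differ in kind between arms. Section 10.3 itself expects crossover mainly from treatment on recovery to early treatment.

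The replacement sentence is a second, separate conflict. Replacement restores the number recruited but does not recover the lost outcome, and it makes the loss less visible.

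**Working it through.** **1. The passages side by side**

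| Question | 7.8 | Elsewhere |
|---|---|---|
| May a participant leave the trial for a significant deviation? | Yes, at the investigator's decision | 10.3: stays whatever treatment is received |
| What ends outcome collection? | Not stated | 10.1: only withdrawal of consent |
| Who is replaced during recruitment? | Any participant who withdraws | 10.2.1 and 13.1: only those refusing use of their data |

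Rows 1 and 3 are direct contradictions. Row 2 is an ambiguity that 10.1 resolves in favour of retention.

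**2. The plan's own sample size**

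Inputs from 10.3: two-sided 5%, 80% power, 1:1 allocation, OR 1.7, mRS distribution (0 to 6) of 17, 10, 6, 19, 11, 10 and 27%. The Whitehead formula without the tie term gives

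n per arm = 6(1.960 + 0.842)² / (ln 1.7)² = 167.3,

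which agrees with the stated 167. The margin up to 346 is 346 − 334 = 12 patients (3.5%). The plan gives it to losses to follow-up (<2%) and crossovers (2%). No allowance is stated for investigator-led discontinuation. The point does not contest 346.

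Power is a minor matter. Using the tie-corrected formula at 173 per arm, losing 2% of outcomes without replacement gives 79.3% and losing 5% gives 78.0%, against 80.1% with none lost.

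**3. Possible bias (assumed; the documents give no rate)**

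Take no true effect and the design distribution in both arms. Remove a fraction x from one arm, renormalise, and refit the proportional odds model. Two patterns:

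- *Upper end:* everyone removed has mRS 6 and is missing from the analysis. With c the cumulative proportion at or below a cut, the odds ratio at that cut is (1 − c) / (1 − x − c). For x = 5% in the early arm this is 0.83/0.78 = 1.06 at 0 versus 1–6, and 0.27/0.22 = 1.23 at 0–5 versus 6. The fitted common OR is 1.127.
- *Milder:* those removed from the deferred arm have odds of a better mRS three times, or one third, those of the design distribution.

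| Removed from one arm | Patients of 173 | Milder pattern, common OR | All deaths, early arm | All deaths, deferred arm |
|---|---|---|---|---|
| 2% | about 3 | 1.02 or 0.98 | 1.047 | 0.955 |
| 5% | about 9 | 1.06 or 0.95 | 1.127 | 0.888 |

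The approximate shift in the test statistic is z = ln(OR) × √[173(1 − Σp³)/6], with Σp³ = 0.035. At 2% the two-sided type I error is about 5.1% (milder) to 5.7% (all deaths). At 5% it is about 6% to 9.6%.

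**The case against.** The strongest reply is that the rest of the protocol already points to retention. Section 10.1 excepts only withdrawn consent and 10.3 keeps everyone. Section 13.5 deals with unintentional deviations by documenting, reporting and corrective action, and does not mention removing the participant. Section 13.1 warns against unnecessary withdrawals. Sections 7.3 and 7.4 record the treatment actually received in both arms, and a separate per-protocol analysis makes sense only if deviators stay in the main one. Section 7.8 never says that outcome collection ends. All of this stands. It shows what was intended, and so how the conflict should be resolved, but it does not remove the conflict.

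Three stronger readings are tempting and are not supported:

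- *That 7.8 breaks an intention-to-treat analysis promised in 10.3.* Section 10.3 does not use that term; 10.2.1 names a modified intention-to-treat analysis. Harm follows only if sites act on 7.8 by stopping follow-up.
- *That an OR near 1.13 is to be expected.* That figure needs known deaths to vanish from the analysis. Death is coded 6 and data up to withdrawal are used (10.2.1). Mortality is collected at day 30 and 12 months (7.7), deaths that sites learn of are reported as SAEs (9.6), and uncertain cases are pursued through the GP and death certification (10.3). The 5% rate also exceeds the plan's own 2% crossover estimate.
- *That every discontinued participant is replaced.* The sentence in 7.8 applies only during recruitment and speaks of a participant who withdraws. Extending it to investigator-led removal is an inference. Nor does replacement in itself bias the comparison; the missing outcome does.

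**Conclusion.** The point holds as two contradictions in the text, and neither depends on a calculation. Section 7.8 permits discontinuation from the trial where 10.1 and 10.3 provide for retention, and its replacement sentence is wider than the rule in 10.2.1 and 13.1.

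The consequence is conditional. If follow-up stops under 7.8, living participants leave the primary analysis, possibly at different rates by arm. On the assumptions shown, the common OR moves by about 2% (2% removed, milder pattern) to 13% (5% removed, all of them deaths missing from the analysis). At the plan's own 2% it moves by 2% to 5%. These figures illustrate sensitivity; they do not forecast bias. The reason to act is that outcomes not collected cannot be fully recovered at analysis, whereas correcting the wording is simple.

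**What to change.** Reconcile 7.8 with 10.1, 10.2.1, 10.3 and 13.1:

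1. State in 7.8 that any participant who has not withdrawn consent, personally or through a consultee, is followed to 12 months for mRS and vital status and analysed in the randomised arm, whatever treatment was received and whatever deviation occurred. Termination of the trial by the sponsor is the one exception.
2. Delete the general replacement sentence in 7.8 and refer to the single rule in 10.2.1 and 13.1, under which only a participant who refuses use of the data is replaced, while recruitment is open.

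This concerns follow-up and analysis only. It sets no rule on when the allocated treatment strategy may be changed.

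Cost: a protocol wording amendment and a reminder to sites. No additional patients or visits, and the sample size of 346 is unchanged.
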